**A. Attribution of Adverse Events:**

Adverse events will be monitored for each subject participating in the study and attributed to the study procedures / design by the principal investigator ([name]) according to the following categories:

- a.) Definite: Adverse event is clearly related to investigational procedures(s)/agent(s).
- b.) Probable: Adverse event is likely related to investigational procedures(s)/agent(s).
- c.) Possible: Adverse event may be related to investigational procedures(s)/agent(s).
- d.) Unlikely: Adverse event is likely not to be related to the investigational procedures(s)/agent(s).
- e.) Unrelated: Adverse event is clearly not related to investigational procedures(s)/agent(s).

**Plan for Grading Adverse Events:** The following scale will be used in grading the severity of adverse events noted during the study:

- a) Mild adverse event
- b) Moderate adverse event
- c) Severe

**Plan for Determining Seriousness of Adverse Events:**

**Serious Adverse Events:** In addition to grading the adverse event, the PI will determine whether the adverse event meets the criteria for a Serious Adverse Event (SAE). An adverse event is considered serious if it:

- A is life-threatening OR
- B. results in in-patient hospitalization or prolongation of existing hospitalization OR
- C. results in persistent or significant disability or incapacity OR
- D. results in a congenital anomaly or birth defect OR
- E. results in death OR
- F. based upon appropriate medical judgment, may jeopardize the subject's health and may require medical or surgical intervention to prevent one of the other outcomes listed in this definition, OR
- G. adversely affects the risk/benefit ratio of the study

An adverse event may be graded as severe but still not meet the criteria for a Serious Adverse Event. Similarly, an adverse event may be graded as moderate but still meet the criteria for an SAE. It is important for the PI to consider the grade of the event as well as its "seriousness" when determining whether reporting to the IRB is necessary.

**Plan for reporting Reportable Adverse Events and other unanticipated problems involving risks to subjects or others to the IRB**

The principal investigator will report the following types of events to the IRB: a) adverse events that are serious or life-threatening AND unanticipated (or anticipated but occurring with a greater frequency than expected) AND possibly, probably or definitely related to the

drug/device/intervention; and b) other unanticipated problems involving risks to subjects or others.

These adverse events or unanticipated problems involving risks to subjects or others will be reported to the IRB in accordance with IRB Policy 710, using the appropriate forms found on the website.

**Plan for reporting adverse events to co-investigators on the study, as appropriate the protocol's research monitor(s)**

For the current study, the following individuals, funding, and/or regulatory agencies will be notified (choose those that apply):

All Co-Investigators listed on the protocol.

National Institutes of Health

The principal investigator ([name]) will conduct a review of all adverse events upon completion of every study subject. The principal investigator will evaluate the frequency and severity of the adverse events and determine if modifications to the protocol or consent form are required.

**12. Statistical Considerations:** Describe the statistical analyses that support the study design.

**Primary endpoints:** Primary endpoints include (a) HbA1C levels and CGM measures of glycemia; (b) baseline intracellular fructose and glutathione levels at 0, and 12 weeks; (c) intracellular fructose and glutathione levels following hyperglycemic clamp at 0 and 12 weeks.

**Secondary endpoints:** Concentrations of hormones and polyol metabolites will be correlated with structural changes/inflammatory changes on MRI.

**Sample size:** Because endogenous intracellular fructose production in the brain has never been shown in humans, the studies described in this proposal are exploratory studies. As such, sample sizes and statistical comparisons may not provide adequate power for definitive hypothesis testing. Because intracellular polyol levels will likely be equal to or higher than CSF levels, we expect that the percentage changes as measured by MRS will match those (or be even larger) than observed in CSF.

**Statistical analysis:** Before statistical testing, all variables will be tested for normality of distribution. For between-group comparison, ANOVA and t-tests will be used for continuous variables. Within subject comparisons at baseline and following hyperglycemia will be made with paired t-tests (parametric) and Mann-Whitney U (non-parametric) as well as repeated measures ANOVA as appropriate.

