### SECTION V: RESEARCH PLAN

- Statement of Purpose:** State the scientific aim(s) of the study, or the hypotheses to be tested.  
Growing evidence suggests that fructose is linked to the development of obesity and diabetes. Studies investigating the central nervous system (CNS) effects of fructose have shown that fructose and glucose have distinct metabolic effects in the brain. While intraventricular glucose infusion into the brain decreases feeding in rodents, intraventricular fructose infusion has the opposite effect to promote feeding. Moreover, our research group has shown using functional MRI in humans that ingestion of fructose and glucose has differential effects on cerebral blood flow in specific brain regions that influence eating behavior.

Recently, we have found that glucose is converted to fructose in the CNS via the polyol pathway (glucose→sorbitol→fructose). We found that fasting cerebrospinal fluid (CSF) fructose levels obtained at the time of spinal anesthesia in pregnant women undergoing elective

caesarean section are nearly 20-times higher than plasma levels. CSF sorbitol levels were also nearly 10-fold greater than plasma levels further supporting the presence of an active polyol pathway in the CNS. Furthermore, CSF fructose levels correlated positively with CSF glucose levels ( $p = 0.453$ ,  $p = 0.02$ ).

**Specific Aim:** To investigate whether longer-term improvement of glycemic control in poorly controlled diabetes patients with a 12-week intensification of their diabetic treatment regimen will lead to decreased polyol pathway activity.

**Hypothesis:** Polyol pathway activity will decrease in diabetic individuals who undergo intensification of their diabetes treatment regimens as reflected by lower baseline brain intracellular fructose levels and higher intracellular glutathione levels. Furthermore, following longer-term improved glycemic control, patients may also have down-regulation of the pathway as reflected by decreased production of intracellular fructose in response to hyperglycemic clamp.

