15 T2DM subjects and 15 T1DM subjects with chronic hyperglycemia (HbA1C > 7.5%) will participate in a 12-week intervention study aimed at reducing their A1C levels. By lowering their glucose levels, we expect to also decrease activity through the polyol pathway. Subjects will receive exercise and dietary counseling in accordance to guidelines established by the American Diabetes Association. In addition, all patients will have their diabetes regimens adjusted on a weekly basis to achieve a target blood glucose level based upon data from the patients performing self-monitoring of blood glucose (SMGB).

At 0 and 12 weeks, subjects will undergo baseline MRS scan at 4T to measure intracerebral glucose, fructose, and glutathione. Participants may also be invited to participate in an overnight admission to normalize blood glucose levels, and a hyperglycemic clamp. During each of these two scans, plasma glucose, fructose, insulin, HbA1c, and fructosamine levels will be measured concurrently. One week prior to the week 0 and week 12 MRS scans, subjects will be asked to wear a CGMS (Free style libre) to continuously monitor their interstitial blood glucose levels and record their food intake in a food log. After first placing the CGM prior to the week 0 scan, the system is removed after 14 days and then reinserted for 14 days before the week 12 MRS scan.

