**MRI and MRS scanning:**

Subjects will undergo MRS scanning at 4T at 0, and 12 weeks of the study. Scan time is ~45 minutes. After a T1 weighted MRI for anatomy (gray/white/CSF segmentation), glucose and fructose concentrations will be obtained from ~3X3X3 cc voxels. Signals from respective voxels are isolated using a MEGA PRESS-based sequence. Metabolite levels are measured by spectral fitting using a simulated basis set and referenced to total voxel water signal and creatinine to determine concentration.

[figure not shown]
During each of these two scans, plasma glucose, fructose, insulin, HbA1c, and fructosamine levels will be measured concurrently.

A nurse experienced with working in a MRS environment will be with subjects at all times. Vital signs including heart rate and blood pressure will be monitored prior to scanning. If patients express discomfort or anxiety and ask to be removed from the scanner, the session will be immediately terminated.

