**Optional Hyperglycemic clamp:**

Prior to MRS scanning at weeks 0 and 12 Subjects may also be invited to participate in an optional overnight admission to normalize blood glucose levels the night before scanning and then a hyperglycemic clamp the following morning.

Subjects will be admitted in the evening prior to MRS scan day (~ 6 PM) to the YNHH research unit, all of their diabetic medications will be held and they will be placed on an insulin drip beginning at 8PM to maintain blood sugar levels at ~90-100 mg/dl until 7AM the next morning. The next morning, participants will be taken to the MRRC for MRS scanning. Following the 45 minute

baseline scan, subjects will remain in the scanner for continuous scanning during the hyperglycemic clamp (see figure). An infusion of 20% dextrose at a variable rate to maintain plasma glucose levels at 220 mg/dL for 4 hours. Glucose infusion rates will be adjusted in response to plasma glucose levels measured every 5-10 minutes. Subjects will be able to take breaks as needed during the 3 hours hyperglycemic clamp and MRS scan. At baseline, 2 and 4 hours, plasma samples will also be obtained for fructose, sorbitol, insulin levels and other hormonal markers.

**Continuous glucose monitoring system (CGMS) and Food logs (at -1, and 11 weeks):** One week prior to the MRS scans at 0 and 12 weeks, subjects will be asked to wear a CGMS (Free style libre) to continuously monitor their interstitial blood glucose levels and record their food intake

**Blood collection for platelet and inflammation analysis:** Participants will also have blood collected (~80 cc) for analysis of polyol pathway activity in platelets as well as for changes in inflammatory markers such as cytokines IL-6, TNF-alpha at weeks 0, and 12 weeks.

**Optional Specimens for Future Storage:** Subjects will be asked to give permission for the storage of any blood obtained during the study that will not be used for the above noted analysis

**4. Genetic Testing** N/A

**5. Subject Population:** Provide a detailed description of the types of human subjects who will be recruited into this study.

15 T2DM subjects with HbA1C > 7.5%

15 T1DM subjects with HbA1C > 7.5%

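### Endpoint (c) reads a smaller brain fructose response to the clamp as pathway down-regulation, but the analysis makes no reference to brain glucose, which the clamp does not fix

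*Combined protocol and SAP*

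**What the plan says.** All references are to Section V of the combined protocol and SAP.

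- **Item 1, Statement of Purpose.** The pathway runs from glucose through sorbitol to fructose. After predicting lower baseline fructose, the hypothesis adds that "patients may also have down-regulation of the pathway as reflected by decreased production of intracellular fructose in response to hyperglycemic clamp".
- **Item 1, design summary.** At weeks 0 and 12 subjects have a "baseline MRS scan at 4T to measure intracerebral glucose, fructose, and glutathione". The summary expects lower glucose to bring lower pathway activity.
- **Item 3, MRI and MRS scanning.** In each scan "glucose and fructose concentrations will be obtained from ~3X3X3 cc voxels".
- **Item 3, Optional Hyperglycemic clamp.** After the baseline scan, "subjects will remain in the scanner for continuous scanning during the hyperglycemic clamp". Dextrose is infused to "maintain plasma glucose levels at 220 mg/dL for 4 hours". The same section, and the risk section in item 9, also give 3 hours. These statements need to be reconciled, because the length of exposure bears on the same endpoint.
- **Item 12, Statistical Considerations.** Endpoint (a) is "HbA1C levels and CGM measures of glycemia". Endpoint (b) is baseline brain fructose and glutathione. Endpoint (c) is "intracellular fructose and glutathione levels following hyperglycemic clamp at 0 and 12 weeks". The secondary endpoint relates hormones and polyol metabolites to MRI findings. The methods are t-tests, Mann-Whitney U and ANOVA, with no covariate, ratio or model of fructose on brain glucose.

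**The concern.** Down-regulation is a claim about the pathway: less product for the same substrate. The clamp makes the two visits comparable in plasma glucose, but the substrate for brain fructose is brain glucose, which also depends on how much glucose gets into the brain. If that amount differs between week 0 and week 12 at the same plasma level, fructose can fall with no change in the pathway, or a real change in the pathway can be hidden. This holds whether the level during the clamp or the rise from baseline is analysed. At stake is the mechanistic reading of endpoint (c), not the fact of higher or lower fructose.

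**Working it through.** The plan states no power, alpha, effect size or standard deviation for this endpoint, so there is no figure of its own to reproduce. The check is of the text, followed by illustrations on stated assumptions.

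**1. What is measured against what is analysed**

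| Quantity | Measured | Role in item 12 |
|---|---|---|
| Plasma glucose | Held at 220 mg/dL in the clamp | None as an endpoint |
| Brain fructose | Baseline and clamp | Endpoints (b) and (c) |
| Brain glutathione | Baseline and clamp | Endpoints (b) and (c) |
| Brain glucose | Baseline stated; clamp implied by continuous scanning | None named |

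**2. Does fructose track glucose in the sponsor's own data?** Item 1 reports a correlation of 0.453 (p = 0.02) between CSF fructose and CSF glucose. With t = r√((n−2)/(1−r²)), n = 26 gives t = 0.453 × √(24/0.795) = 2.49 and p = 0.0201, so the figures fit an n of about 26, which the document does not state. r² = 0.21. This supports dependence of fructose on glucose between people. It comes from fasting pregnant women and gives neither the slope nor the within-patient relation in diabetes.

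**3. How a change in brain glucose would pass through.** Suppose the fructose response is F = k·G^b, with k the pathway activity and G the brain glucose response. Between visits, F₁₂/F₀ = (k₁₂/k₀)(G₁₂/G₀)^b. The exponents and percentages below are assumed.

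| Pathway (k₁₂/k₀) | Brain glucose (G₁₂/G₀) | b | Fructose | Fructose/glucose |
|---|---|---|---|---|
| 1.00 | 0.80 | 0.5 | 0.80^0.5 = 0.89 | 0.80^(−0.5) = 1.12 |
| 1.00 | 0.80 | 1 | 0.80 | 1.00 |
| 1.00 | 0.80 | 2 | 0.80² = 0.64 | 0.80 |
| 0.80 | 1.25 | 1 | 0.80 × 1.25 = 1.00 | 0.80 |

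The first three rows show fructose falling with an unchanged pathway. The last, with figures chosen to cancel exactly, shows a real fall hidden. The final column shows that the ratio is neutral only when b = 1.

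**4. How often a fructose-only test would mislead.** The simulation used 4,000 runs per scenario with the pathway unchanged, b = 1, SD of log brain glucose change 0.15, residual SD of log fructose change 0.3 to 0.5, and a two-sided paired t-test at 0.05. None of these inputs is from the documents. The entries are the percentage of trials with a significant result.

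| Lower brain glucose at week 12 | n = 8 | n = 15 | n = 30 |
|---|---|---|---|
| 10% | 8–13% | 11–21% | 19–39% |
| 20% | 19–37% | 34–68% | 61–94% |
| 30% | 39–72% | 70–97% | 96–100% |

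A larger sample makes the misleading result more frequent. A fructose/glucose ratio stays at about 4–6% in the same runs, but only because b = 1 was built in, so this does not validate the ratio.

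**5. What adjustment can and cannot recover.** With the simulation's assumed measurement noise of 0.10 for brain glucose, the reliability of the measured glucose change is 0.15²/(0.15² + 0.10²) = 0.0225/0.0325 = 0.69. A regression slope is attenuated by that factor. For a 20% fall in brain glucose (log 0.80 = −0.223) and an unchanged pathway, the adjusted fructose change would still show −0.223 × 0.31 = −0.069, a false fall of about 7% in place of 20%. Adjustment helps but does not remove the ambiguity.

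**The case against.** - **Nothing in the documents says that brain glucose at a fixed plasma level changes over 12 weeks.** This stands. The confounding is possible but not shown, and every size above is illustrative.
- **A reader might infer that the two explanations cannot be separated at all.** The documents do not support that. Brain glucose is measured, the endpoint list is not worded as exhaustive, and the general analysis sentences could cover a stand-alone comparison of brain glucose. What is missing is any planned link between glucose and fructose.
- **A reader might extend the point to endpoint (b), or take the fructose-to-glucose ratio as the answer.** Neither follows. Item 1 intends baseline fructose to fall because glucose falls. Item 2 (Background) says that only a small share of glucose enters the pathway at normal levels but up to 30% in hyperglycemia, so the ratio would be expected to move with glucose itself. Overnight normalization is optional, so baseline scans without it are taken at whatever glycemia treatment has produced, and the ratio could fall with an unchanged pathway.
- **The hypothesis is tentative, the clamp is optional and the study is exploratory.** True, and this limits the weight of the point. But the exploratory caveat in item 12 is about power, and more subjects would not resolve this ambiguity.
- **Same-voxel glucose during the clamp is not stated outright.** Also true. The scanning section speaks of voxels in the plural, and the clamp section lists no metabolites. It is a reasonable inference that the plan should make explicit.

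**Conclusion.** The concern holds for endpoint (c). As planned, a smaller fructose response at week 12 would support a statement about fructose production at a given plasma glucose. It would not by itself support down-regulation, because the substrate in the brain is neither fixed nor used in the analysis. The error could run in either direction. Its size is unknown. The illustrations rest on assumed exponents, variances and changes in brain glucose, and show only that a moderate change would matter. The conclusion itself rests on two things in the documents: fructose is formed from glucose in the plan's own pathway, and the clamp target is a plasma value. It does not touch the study design or endpoint (b). This is a cheap improvement.

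**What to change.** In Section V, item 12:

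1. State that brain glucose is quantified during the clamp scans as well as at baseline, and say whether it comes from the same voxel as fructose.
2. Report the week 0 to week 12 change in brain glucose, with a confidence interval, beside the change in fructose.
3. Add a supportive analysis of the clamp fructose response adjusted for the brain glucose response. Options are a regression of the week 0 to 12 change in fructose response on the change in brain glucose response, or a mixed model with brain glucose as a time-varying covariate. Either estimates the slope and does not force proportionality.
4. Conclude down-regulation only if the fructose fall is not explained by a fall in brain glucose. If the two cannot be separated, describe the result as lower fructose production.
5. Keep absolute fructose as the primary measure for endpoint (b), and do not use the baseline fructose-to-glucose ratio as evidence of down-regulation.

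The cost is a few lines of text and, provided glucose can be quantified from the clamp spectra, no added scans or visits. Statistically, the adjusted estimate will have a wider interval in an optional-clamp subset of at most 30, and measurement error in brain glucose will leave some of its effect unadjusted. That is why item 2 should always be read with item 3.

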#### Study design:

**Subjects:** 15 T2DM subjects and 15 T1DM subjects with HbA1C > 7.5% will be recruited from Yale New Haven Hospital and the greater New Haven area.

**Inclusion criteria:** Age 18- 65 yrs, BMI  $\geq 18$  kg/m^2, and weight less than 285 pounds (upper limit of scanner),

**Exclusion criteria:** Creatinine > 1.5 mg/dL, Hgb < 10 mg/dL, hematocrit of 37 % for males participants and 33 % for female participants, ALT > 3 x ULN, , untreated thyroid disease, uncontrolled hypertension, known neurological disorders, untreated psychiatric disorders, malignancy, bleeding disorders, current or recent steroid use in last 3 months, illicit drug use; for women: pregnancy, actively seeking pregnancy, or breastfeeding; inability to enter MRI/MRS (per standard MRI safety guidelines).

**Screening visit:** Volunteers will be screened at the YNHH Research Unit (HRU) with a medical history and exam including detailed neurologic exam. Blood tests will be collected for A1C, ALT, TSH, Hematocrit. Less than 35 mL of blood will be drawn for blood work. Women will undergo urine pregnancy testing. Subjects will be required to give us information about their substance use/HIV status because this can affect brain glucose metabolism.

**Intensification of Insulin regimens:** The intensification of the diabetes regimens will be managed by [name], a fully trained attending endocrinologist, and will follow the general strategies outlined in the Position Statement of the American Diabetes Association and the European Association for the Study of Diabetes. All participants will receive exercise and dietary counseling from [name], a nutritionist and registered dietician with extensive

experience with working with individuals with diabetes and obesity. Participants will communicate with a nutritionist regularly over the course of the 12-week study.

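### The normality check does not name the within-subject differences, and for paired comparisons it can lead to Mann-Whitney U, which ignores the pairing and can cost substantial power

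*Combined protocol and SAP*

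**What the plan says.** The relevant text is the statistical analysis paragraph of Section V, item 12. It opens: "Before statistical testing, all variables will be tested for normality of distribution". For groups it continues: "For between-group comparison, ANOVA and t-tests will be used for continuous variables". Comparisons within subjects, described there as at baseline and after hyperglycemia, "will be made with paired t-tests (parametric) and Mann-Whitney U (non-parametric"), "as well as repeated measures ANOVA as appropriate".

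The primary endpoints in the same item include two paired brain measures: "baseline intracellular fructose and glutathione levels at 0, and 12 weeks", and "intracellular fructose and glutathione levels following hyperglycemic clamp at 0 and 12 weeks". The number of pairs follows from Section V, item 3: "15 T2DM subjects and 15 T1DM subjects with HbA1C > 7.5% will be recruited". That gives at most 15 pairs per diabetes type and 30 overall, and possibly fewer after the clamp, which is optional.

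The documents do not name a normality test or its level. They do not say at which time point a variable is checked, whether change scores are among the variables, or what follows when one time point passes and the other fails. The week 0 to week 12 comparison is not expressly named in the within-subject sentence; I take it to be covered.

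**The concern.** A paired t-test works on one number per subject, the difference. Its normality assumption concerns those differences. Raw levels can be strongly skewed because subjects differ from one another, while the changes within subjects are close to normal.

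A normality check placed before testing, followed by a parametric and a non-parametric option, most naturally means that the check picks the test. Applied to raw levels, it answers the wrong question for a paired comparison. It also yields two verdicts per pair, with no rule for combining them.

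The larger cost comes from where a failed check leads. Mann-Whitney U compares two independent samples. Used on two visits by the same people, it leaves the between-subject spread in the comparison, which the pairing would have removed. The comparisons exposed to this include the study's central one, the 12-week change in brain fructose and glutathione.

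**Working it through.** The plan states no alpha, effect size, variance or power, so it has no figure to reproduce. The check below shows what the text permits under stated assumptions.

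**From the documents:** two paired time points; 15 or 30 pairs; paired t-test or Mann-Whitney U.

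**Assumed:** Shapiro-Wilk at 0.05 as the normality check; two-sided tests at 0.05; week 0 levels log-normal with mean 1 and CV 50%, so the log-scale variance is ln(1 + 0.5²) = 0.223; changes independent of level and exactly normal with SD 0.3; true shift 0.22.

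**Step 1. Power of the paired t-test, closed form.** The standardised change is 0.22/0.3 = 0.733. The noncentrality is 0.733 × √15 = 2.84 with 15 pairs and 0.733 × √30 = 4.02 with 30. With critical values 2.145 (14 df) and 2.045 (29 df), power is 75.2% and 97.3%.

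**Step 2. Why dropping the pairing costs so much.** The variance is 0.5² = 0.25 at week 0 and 0.25 + 0.3² = 0.34 at week 12. Treated as independent samples, the mean difference has standard error √(0.25 + 0.34)/√n = 0.768/√n. Paired, it is 0.3/√n. The ratio is 0.768/0.3 = 2.56.

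**Step 3. Simulation of the whole procedure** (10,000 data sets per sample size; Monte Carlo standard error at most 0.5 points).

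| Quantity | 15 pairs | 30 pairs |
|---|---|---|
| At least one visit fails the check | 40% | 71% |
| Both visits fail | 13% | 31% |
| The visits disagree | 26% | 40% |
| The differences fail | 5% | 5% |
| Power, always paired t | 75% | 97% |
| Power, Mann-Whitney U if either visit fails | 50% | 52% |
| Power, Mann-Whitney U only if both fail | 66% | 77% |
| Power, signed-rank if either visit fails | 74% | 97% |

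A separate run with other random numbers gave 76% falling to 50%, and 98% falling to 53%. The differences are normal by construction, so their 5% failure rate is just the level of the check. The two Mann-Whitney rows show that the missing tie-break matters: the same data give 50% or 66% power with 15 pairs, and 52% or 77% with 30, depending on a rule that the plan does not state.

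**Step 4. The opposite case.** Take normal week 0 levels with SD 1, skewed changes (a centred exponential with SD 0.4) and a shift of 0.3. Both visits pass while the differences fail in 62% of data sets with 15 pairs and 88% with 30, so the comparison stays on the paired t-test. For a true mean change of zero, the paired t-test has type I error 8.7% and 7.8%. Signed-rank has 11.1% and 16.2%, because it assumes symmetric differences. Power is 74% and 92% for paired t, against 0.4% and 1.7% for Mann-Whitney U. In this setting, staying on the t-test is not the worse outcome.

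**The case against.** **The routing is inferred.** The text has no explicit switch and says only that methods are used as appropriate. All variables could include change scores. This stands: the documents support a rule that is unspecified and permits misrouting. A reader might infer that the plan demonstrably sends outcomes to the wrong test in both directions, but the text does not go that far. Including change scores would not settle the matter either, because each pair would then have three verdicts and still no tie-break.

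**The harm comes from the fallback.** This also stands. With a signed-rank fallback, about one point of power is lost. The per-variable check by itself would be a minor matter; it is the combination with Mann-Whitney U that costs power.

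**The opposite direction shows no damage.** Step 4 agrees. Skewed changes often go unflagged, but remaining on the paired t-test was preferable to the plan's alternative.

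**The check has other uses.** The distribution of the measured variables can matter for the between-group comparisons and for the secondary correlations, and this point does not reach them.

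**The illustration favours the concern.** It assumes normal changes on the raw scale. If changes are multiplicative, raw differences are themselves often non-normal: with within-subject log SD of 0.15 to 0.40, Shapiro-Wilk flags them in 20–29% of data sets with 15 pairs and 36–49% with 30. Some flags would then be justified. This is a reason to fix the scale in advance, not to keep the switch.

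**The study is exploratory.** Item 12 says so and warns of limited power. That limits the severity, but it does not justify discarding power that the paired design already provides.

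**Conclusion.** The point holds in a limited form. For paired comparisons, the plan does not say that the differences are what is checked, gives no rule when time points disagree, and names a fallback that ignores the pairing. Under the assumptions above, and if failure at either visit triggers the switch, power falls from about 75–76% to 50% with 15 pairs and from about 97–98% to 52–53% with 30. If both visits must fail, it falls to 66% and 77%. These figures are illustrative; the documents give no variances from which to estimate the loss in this trial.

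Two stronger conclusions are tempting and not supported. One is that false positives are inflated. In the log-normal setting with no true change, a 6,000-data-set run of the either-visit rule rejected in 3.2% (15 pairs) and 1.6% (30 pairs), so it errs towards missing effects. The other starts from 12 checks (six primary outcomes at two visits), each at 5% on normal data, which give 1 − 0.95^12 = 46% for at least one flag. A reader might take this as the chance of a wrong result. It assumes independent checks, although visits of the same subject are correlated, and it counts flags rather than wrong conclusions.

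Severity is modest: worth correcting, in a study that calls itself exploratory.

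**What to change.** For the paired comparisons only:

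1. Drop the normality check as a means of choosing the test.
2. For each primary outcome, pre-specify a t-based analysis of the within-subject change as the main result. Name both comparisons: week 12 minus week 0, and the change in response to the clamp.
3. Fix the scale of each outcome in advance, for example log for concentrations and raw for HbA1c.
4. Inspect the differences by plot.
5. Report one pre-named paired rank test of the same differences, such as Wilcoxon signed-rank, as a sensitivity result in place of Mann-Whitney U. Do not switch the main result because of it.

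Moving the check to the differences while keeping Mann-Whitney U would not be enough. In the skewed-change setting of step 4, that gives power of only 27% with 15 pairs and 5% with 30.

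The cost is about two sentences in item 12 and one extra analysis per outcome. No new data or subjects are needed.
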